5.3.2 Restrictions

Subjects will be administered the drug products in sitting posture. Subjects will avoid severe physical exertion during sampling hours.

Methylxanthine-containing food or beverages and grapefruit, orange, cranberry or juices of these three fruits are not allowed for 24 hours before and during the entire sampling days. Consumption of alcohol-based products is restricted for 24 hours before and during the entire sampling days.

Any concomitant medications (including non-prescription medication, multi-vitamin preparations or herbal medications) are prohibited during the whole study (from Screening Visit to the Follow-Up Visit).

5.3.3 Criteria for Subjects' Withdrawal from the Study

The Investigator may withdraw a subject from the study based on following reasons:

1. Withdrawal of subject's consent;
2. Significant protocol violation, such as non-compliance with restriction regarding alcohol and drug use, and non-adherence to the the fasting condition;
3. Adverse events, as assessed by the Investigator to affect the subject safety or the outcome of the study endpoints;
4. Difficulties with blood collection;
5. Subject who vomits anytime during PK blood sampling periods will be excluded from the remainder of the study (including the rest of the periods if the adverse event occurred in the earlier ones). The subject will be advised to remain in the clinic for the rest of the confinement period for observation and so any safety related study procedures can be carried out;
6. Subject reports adverse events of diarrhea (more than three episodes of loose stools) in any PK blood sampling period, which could render the plasma concentration-time profile unreliable;
7. Subject is uncooperative during the study;
8. Use of any ongoing or concomitant medication.

Subject may withdraw from the study at any time without any reason. Subjects who do not attend Study Check-In or withdraw during the study will be recorded in the Log Book of Non-Conformities Work. If the subject discontinues from the study at any time after taking

the first dose of the study drug, the CRF would be completed accordingly and drug concentration will be analyzed. If a subject is discontinued early, all termination evaluations will be performed at the time of discontinuation. Details of reasons for premature withdrawal of subjects will be documented in the final study report.

6 STUDY PRODUCTS AND RANDOMIZATION

6.1 Product

TEST DRUG INFORMATION

Each extended release tablet produced by PT Merck Tbk, Jakarta, Indonesia (Glucophage® XR 750 mg Tablet) contains metformin hydrochloride 750 mg.

Batch No. : 2050201
Mfg. Date : 23 April 2017
Exp. Date : 22 April 2019
Batch size : 100,000 tablets

Name and address of manufacturer:
PT Merck Tbk
[name]
[name]
INDONESIA

COMPARATOR (REFERENCE) DRUG INFORMATION

Each extended release tablet produced by Merck Santé, Semoy, France (Glucophage® XR 750 mg Tablet) contains metformin hydrochloride 750 mg.

Batch No. : Y02170
Mfg. Date : 09 November 2016
Exp. Date : October 2019
Reg. No. : DKI1401600214B1

Name and address of manufacturer:
Merck Santé
[name]
[name]
FRANCE

Name and address of importer:
PT Merck Tbk
[name]
[name]
INDONESIA

All drug supplies will be kept in an appropriate locked cupboard which can only be accessed by the Investigator or designated study personnel. Drug accountability records, including study drug storage, handling, dispensing, documentation of administration, return and the return/destruction of the drug will be maintained.

A designated study personnel will record the actual date and time of drug administration to the subjects. In case the study has to be discontinued, the exact date, time and the reason for discontinuation will be documented in the CRF.

6.2 Randomization

[figure not shown]

Figure 1 Flow Chart / Study Design Diagram

The randomization code is tabulated for all subjects according to block randomization with a block size of 4. ⁽⁶⁾ Subjects will be randomly allocated to one of the 2 treatment sequences (TR or RT) based on their assigned subject number. The randomization to a treatment sequence will be performed before the first period of the study.

Each study drug (test and reference drug) will be placed in a sealed envelope indicated with the subject number and its intended period, and segregated in different labelled boxes kept in a limited access drug storage room. The study drugs will be dispensed to the study subjects by an unblinded pharmacist prior to time of dosing. The randomization will be balanced according to subject number and the randomization code will be kept under controlled access. The clinical personnel administering the study drugs and the subjects are not blinded. The randomization code will not be available to the bioanalytical personnel (blinded for bioanalytical facility) till code breaking.

Code breaking will be performed after analysis of all blood samples have been completed but prior to statistical analysis; the Sponsor's green light will be obtained prior to code breaking, upon satisfying pre-defined conditions.

7 STUDY PROCEDURES

7.1 Screening

All assessments previously performed (within 21 days of the first study drug administration) may be used for enrollment purposes as long as a study-specific consent is signed prior to any other study-specific study procedure or assessment. During the Screening Visit the following will be completed:

- Informed consent for study
- Medical history (commencement of safety surveillance)
- Vital signs (blood pressure, pulse rate, respiratory rate, temperature)
- Physical examination and body measurements (height, weight)

- Clinical laboratory tests
 - Liver function : AP, ALT, AST, total protein, albumin and total/direct bilirubin
 - Renal function : serum creatinine and ureum
 - Hematology : hemoglobin, hematocrit, erythrocyte count, leucocyte count, and platelet count
 - Urinalysis : urine chemistry and urine sediment
 - Serology test : HBsAg, anti-HCV, and anti-HIV
 - Blood glucose
- Alcohol breath test and urine test for drug abuse (opiate class, barbiturates, cocaine and metabolites, amphetamines, cannabinoids and benzodiazepines)
- Pregnancy screening (female subjects only)
- 12-lead ECG (remain in a supine position)
- Eligibility (inclusion/exclusion criteria)

7.2 Study Check-In (Day 1)

At Study Check-In, the subjects will report to the clinical site at least 12 hours prior to Day 1 dosing, and will be required to stay for approximately 32 hours after Day 1 dosing. The following will be completed at check-in:

- Alcohol breath test and urine test for drug abuse (opiate class, barbiturates, cocaine and metabolites, amphetamines, cannabinoids and benzodiazepines) will be performed. A urine sample will be collected for a pregnancy screen (female only). Subjects with a positive result will be excluded from the study.
- Subjects will begin fasting at least 10 hours prior to dosing on Day 1.
- Water will be allowed ad lib during fasting till 1 hour prior to dose administration. Throughout the study, standardized meals and beverages will be served. Meals will be the same in content and quantity during each dosing period.

7.3 Treatment Phase

Prior to dosing, the following activities will be completed:

- Vital signs will be measured.
- Pharmacokinetic (PK) sampling will be performed within 60 minutes prior to each subject's scheduled dose time (0-hour blood sample).
- No fluid allowed at least from 1 hour prior to dose administration until 2 hours after dosing except that given at drug administration.

Dosing: each subject will be instructed to take either one tablet of test drug (Glucophage® XR 750 mg Tablet produced by PT Merck Tbk, Indonesia) or one tablet of comparator drug (Glucophage® XR 750 mg Tablet, Merck Sante, France) with 200 mL of water during each dosing period, for a total of 2 doses per subject in the entire study. The actual clock time for each dosing will be recorded in the CRF.

After dosing, the following activities will be completed:

- A fast will be maintained until at least 4 hours after dosing. Water intake will be allowed from 2 hours after drug administration.
- Blood sample collections will be obtained at 1, 1.5, 2, 2.5, 3, 3.5, 4, 4.5, 5, 6, 7, 8, 10, 12, 16, 24, and 32 hours after dosing (\pm 2 minutes for post-dose blood draw).
- Blood pressure, pulse rate, respiration rate, and adverse events will be monitored at pre-dose, 2, 4, 6, 8, 12, 24, and 32 hours after dosing (\pm 30 minutes from the scheduled time point for post-dose vital signs measurements).
- Adverse Event (AE) / Concomitant Medication Query: each subject's well-being will be evaluated.
- Subjects will undergo clinical observation by qualified study personnel for 4 hours after receiving study drug. The Investigator, study physician, and study nurse will be on-site during drug dosing and will stay at the site until all study procedures required in each period is completed, thereafter the study nurse(s) will remain at the site during the subjects' overnight stay.
- Subjects will be instructed not to engage in excessive physical activity during the entire period of the study.
- Lunch will be provided at approximately study hour 4.
- Dinner will be provided at approximately study hour 10.
- Meals/snacks served after study hour 10 will be scheduled by the clinic.
- Subjects who experience vomiting will be treated at the Investigator's discretion.

7.3.1 Study Meals

- Food intake is standardized during the sampling days. Meals will be the same in composition and quantity during each dosing period.
- Methylxanthine-containing food or beverages and grapefruit, orange, cranberry or juices of these three fruits are not allowed for 24 hours before and during the entire sampling day.

7.4 Follow-Up Visit

Follow-up procedures will be performed after the last study activity in the second dosing period, and completed within 7 days after the last blood sampling. Procedures will include physical examination, assessment of vital signs (blood pressure, pulse rate, respiratory rate and temperature), body measurements (height and weight), ECG, clinical laboratory tests (liver function, renal function, blood glucose, hematology, urinalysis), and adverse event evaluation.

If a subject who has received at least one dose of the study drug withdraws prematurely, the Follow-Up Visit will need to be completed within 7 days after his/her last blood sampling.

8 SAFETY ASSESSMENTS

The safety profile of the study drug will be assessed for all enrolled subjects through the recording, reporting and analyzing of baseline medical conditions, physical examination

findings, vital signs (i.e. systolic and diastolic blood pressure, pulse rate, and respiration rate), 12-lead ECG, hematology and biochemistry laboratory tests including urinalysis, and AEs. See section 12.1.2 Clinical Laboratory Assessments, and section 12.1.3 Vital Signs, Physical Examination, ECG and Other Assessments for details.

Comprehensive assessment of any apparent toxicity experienced by the subject will be performed throughout the course of the study, from the time the subject signs on the informed consent form. Study site personnel will report any AE to the Sponsor, whether observed by the Investigator or reported by the subject.

9 PK SAMPLE COLLECTION AND HANDLING PROCEDURES

9.1 PK Sample Collection Schedule

- A 10 mL blood sample (control) will be drawn by venepuncture immediately before drug administration.
- Subsequent blood samples will be drawn 5 mL each at 1, 1.5, 2, 2.5, 3, 3.5, 4, 4.5, 5, 6, 7, 8, 10, 12, 16, 24, and 32 hours after drug administration (± 2 minutes for post-dose blood draws).
- 18 blood samples will be collected in each dosing period for pharmacokinetic analysis.
- Blood sampling will be conducted according to Blood Sampling Collection Form. The actual time of sample collection will be documented in the CRF.

9.2 PK Sample Collection and Processing

- For each sampling time point, 5 mL of blood will be collected in vacuum polypropylene tubes containing K₃EDTA using 22G needle.
- The labels for all biological sample collection and storage containers will contain, at a minimum, the subject's number, study number, dosing period, scheduled collection time point.
- Samples will be sequentially collected by direct venepuncture and placed into the centrifuge within 60 minutes of blood sampling at room temperature.
- After collection, samples will be centrifuged at approximately 1538 g (radius of rotor = 86 mm) at room temperature for 15 minutes.
- Plasma will be divided and transferred into two polypropylene tubes.
- Samples will then be stored in a freezer, at approximately $-20^{\circ}\text{C} \pm 5^{\circ}\text{C}$ until transferred to the bio-analytical laboratory.
- In cases where the volume of plasma harvested from the blood sample is insufficient to meet the minimum volume requirement for bioanalysis, the first polypropylene tube will be filled to meet the minimum volume requirement, and any remaining plasma will be transferred to the second polypropylene tube.

9.3 Criteria for Recording and Reporting PK Blood Sampling Deviation

- A window period of ± 2 minutes from the scheduled time point is allowed for all blood draws.

- The actual sampling time will be recorded in the Blood Sampling Form and also in the CRF. Any sampling time deviation will be recorded in the "Blood Sampling Form" and attached to the CRF.
- Time corrections will be done in the dataset prior to performing PK calculations for any deviations to the post-dose blood sampling time points beyond the specified window period.

9.4 Transport of PK Samples

The separated plasma will be stored in pre-labelled polypropylene tubes during each dosing period. These tubes will be stored in the $-20^{\circ}\text{C} \pm 5^{\circ}\text{C}$ freezer located in the clinical site's sample storage room till the end of each period, after which they will be transferred to another $-20^{\circ}\text{C} \pm 5^{\circ}\text{C}$ freezer at the bio-analytical facility during the sample processing and bio-analysis phase, and until long-term stability tests are performed. Stability tests have been conducted to ensure that the analyte in plasma is stable during storage.

10 BIOANALYTICAL SAMPLE ANALYSES

10.1 Analytical Method Validation

Metformin concentrations will be assayed using a validated high-pressure liquid chromatography with ultraviolet detection (HPLC-UV; Waters™, Milford, MA, USA) method with respect to adequate sensitivity, specificity, linearity, recovery, and accuracy and precision (both within and between run). The Lower Limit of Quantification (LLOQ) of metformin obtained from method validation was 10 ng/mL. Stability of the samples under frozen conditions, at room temperature, and during freeze-thaw cycles has also been determined.

The study will start when the analytical method validation has been completed. Validation will be in accordance to the EMA Guideline on Bioanalytical Method Validation, 2011.

10.2 Assay Method

For analysis of drug concentrations, validated high pressure liquid chromatography with ultraviolet detection (HPLC-UV; Waters™, PPD) method will be used.

An aliquot of human plasma sample will be extracted using protein precipitation with an appropriate solvent, then an appropriate volume of sample will be injected to the HPLC-UV system using methylparaben as an internal standard. Calibration standards, controls, and samples will be processed in batches, where each batch consists of two subjects.

All chromatograms in the same batch will be processed automatically by the software using the same processing parameters such as integration, peak to peak amplitude and peak detection. Manual integration will be performed when the automatic integration performed by the data system has an error:

- Software integration limitations
- Complicated chromatography
- Poor resolution or response

10.3 Quantification

Calibration curve is prepared for metformin by least square linear regression ($Y = aX + b$; where X is the concentration of metformin and Y is the peak area ratio of metformin to internal standard).

The concentration of metformin in plasma sample is determined by entering the peak area ratio of metformin to internal standard into the regression line equation of the standard calibration curve of each substance.

10.4 Quality Control

QC samples in duplicate at three concentrations [within 3x of the LLOQ (low QC), in the mid-range (medium QC), and approaching the high end of the range (high QC)] will be incorporated into each run. At least 67% of the QC samples and at least 50% of the QC samples at each concentration level should be within 15% of their respective nominal (theoretical) concentrations.

Incurred sample reanalysis will be conducted according to the EMA Guideline on Bioanalytical Method Validation, 2011.

11 STUDY ANALYSES

All concentration values below the quantification limit (BQL) will be set to zero for all pharmacokinetic and statistical calculations.

If the pre-dose concentration is ≤ 5 percent of C_{max} value in that subject, the subject's data without any adjustments can be included in all pharmacokinetic measurements and calculations. If there are any subjects for whom the pre-dose concentration is > 5 percent of the C_{max} value for the subject in that period, the subject will be dropped from all the study evaluations.

11.1 Parameters of Bioavailability

The following PK parameters will be estimated according to non-compartmental standard methods using the PK software program Pharsight Phoenix WinNonlin (Version 8.0 or higher):

C_{max}	maximum observed plasma concentration
t_{max}	time to reach C_{max}
AUC_{0-t}	area under plasma concentration versus time curve from administration to last observed concentration at time t
AUC_{0-inf}	area under plasma concentration vs time curve extrapolated to infinite time
$t_{1/2}$	terminal phase half-life time

C_{max} and t_{max} will be obtained directly from the observed data.

11.2 Statistical Analysis

Safety data will be evaluated for all subjects who received at least one dose of study medication. The data from subject(s) who received concomitant medication(s) or experienced diarrhea or vomiting during PK blood sampling periods, which could render the plasma concentration-time profile unreliable as stated on section 5.3.3, may be excluded

for that period from the pharmacokinetic analysis and statistical evaluation. The decision to exclude is made before bioanalysis.

Statistical analyses will include data from all subjects who have valid primary endpoints available for both periods of the study. The plasma concentrations obtained from the bioanalytical laboratory for subjects who have been withdrawn from the study due to adverse events or as list on section 5.3.3 will not be used for statistical evaluation.

The statistical method for testing bioequivalence is ANOVA for two-period, two-sequence, two-treatment cross-over comparing AUC_{0-t} and C_{max} after logarithmic (ln) transformation of the original values. The terms to be used in the ANOVA model are sequence, subject within sequence, period, and formulation.

Bioequivalence is concluded if the 90% confidence interval of the Test/Reference geometric means ratio is in the range of 80.00-125.00%, for AUC_{0-t} and C_{max} . This acceptance criterion is according to the Guideline on the Investigation of Bioequivalence, EMA, London, 2010; ASEAN Guideline for the Conduct of Bioequivalence Study, Lao PDR, 2015; and *Indonesian guidelines, Pedoman Uji Bioekivalensi, Badan Pengawas Obat dan Makanan (BPOM), Jakarta, 2015, page 37-38.*

Non-compartmental standard methods computation of PK parameters will be performed. Details will be provided in the final study report. Phoenix® WinNonlin (Version 8.0 or higher) (PPD [REDACTED]) will be used to perform the statistical analyses of AUC_{0-t} and C_{max} using analysis of variance (ANOVA) after transformation of the data to their natural logarithmic (ln) values. Mean treatment differences will be estimated using the ANOVA model above. 90% confidence intervals will be computed for the treatment differences based on the residual error term. Differences and CIs will result in ratios and corresponding CIs after back-transformation.

The difference in t_{max} will be analyzed non-parametrically on the original data using Wilcoxon matched-pairs test.

The $t_{1/2}$ difference will be analyzed using Student's paired t-test or Wilcoxon matched-pairs test depending whether the differences of the paired data were distributed normally or not.

Descriptive Statistic

Arithmetic means, standard deviations, minimum, maximum, median, and coefficients of variation will be calculated for the parameters listed in section 11.1.

Plasma concentration-time profile will be provided in linear and log scale for mean curves with standard deviation and individual curve in each subject.

Demographic data will be provided as summary tables with information of mean, minimum value and maximum value presented.

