5.2 Inclusion Criteria for Study Subjects

1. Subject has provided written informed consent prior to the conduct of any study-related activities.
2. Male and female subjects.
3. Aged between 18 and 55 years, inclusive.
4. Body mass index of 18 to 25 kg/m².
5. Good physical and mental health status, determined on the basis of medical history and physical examination.
6. Vital signs (blood pressure, pulse rate, respiratory rate and body temperature) in sitting position within the normal range or showing no clinically relevant deviation per the Investigator's opinion.

7. All values for laboratory assessments (hematology, clinical chemistry and urinalysis) within the normal range or showing no clinically relevant deviation per the Investigator's opinion.
8. No clinically significant abnormality on 12-lead electrocardiogram (ECG) recording as judged by the Investigator; QTc (Bazett) should be \leq 450 ms.
9. Non-smoker or smoker less than 10 cigarettes per day.
10. Women of childbearing potential (WOCBP) who are not nursing, are not pregnant, and are using highly effective methods of birth control (defined as those, alone or in combination, that result in a low failure rate (i.e., less than 1 percent per year) when used consistently and correctly) for a period of at least one month before and after dosing. Standard birth control methods are considered to be: oral or implanted contraceptive therapy and intra-uterine devices. Female volunteers may also be enrolled if they are postmenopausal (i.e., at least 12 consecutive months of amenorrhea after the last menstrual period) or surgically sterilized/ hysterectomized at least 6 months prior to study participation.
11. WOCBP must have a negative urine pregnancy test at Screening and on each Study Check-In (Day 1 of each dosing period).
12. Negative screen for alcohol and drugs abuse (opiate class, barbiturates, cocaine and metabolites, amphetamines, cannabinoids and benzodiazepines) at Screening and on each admission (Day 1 of each dosing period).
13. Negative screen for Hepatitis B surface antigen (HBsAg), HCV antibodies and/or HIV antibodies.

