5.3 Exclusion and Restriction Criteria for Study Subjects

5.3.1 Exclusion Criteria

Any of the following criteria will exclude the subject from the study:

1. Participation in a clinical trial/study within 90 days prior to Screening.
2. Blood donation (equal or more than 300 mL) or significant blood loss within 90 days prior to first drug administration.
3. Any surgical or medical condition, including findings in the medical history or in the pre-study assessments, or any other significant disease, that in the opinion of the investigator, constitutes a risk or a contraindication for the participation of the subject in the study or that could interfere with the study objectives, conduct or evaluation.
4. History of malignant diseases, except in-situ basal cell skin tumors treated with curative intent.
5. History of surgery of the gastrointestinal tract which could influence the gastrointestinal absorption and/or motility per the Investigator's opinion.
6. History or presence of relevant liver diseases or hepatic dysfunction (laboratory result for liver function test \geq 1.5 ULN).
7. History or presence of renal failure or renal dysfunction based on clinical symptoms and finding (serum creatinine concentration $>$ 1.4 mg/mL).
8. Ascertained or presumptive hypersensitivity to the active drug substance and/or formulations' ingredients; history of anaphylaxis to drugs or allergic reactions in general, which the Investigator considers may affect the outcome of the study.

9. Receipt of any prescription or non-prescription medication within 14 days before the first drug administration, except for hormonal contraceptives in female, and including multivitamins and herbal products (e.g. St John's Wort).
10. Consumption of large quantities of methylxanthine-containing beverages (> 5 cups of coffee/day or equivalent).
11. Consumption of grapefruit, orange, cranberry or juices of these three fruits, 24 hours prior to drug administration.
12. Known lack of subject compliance or inability to communicate or cooperate with the Investigator (e.g., language problem, poor mental status).

This study will be carried out in accordance to the Good Clinical Practice (GCP) standards. Approval from the Ethics Committee will be sought prior to the conduct of the study.

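### Does the concomitant-medication rule remove women on permitted hormonal contraception from the primary PK set?

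*Protocol*

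**What the plan says.** **Entry.** Protocol 5.2, inclusion 10, requires women of childbearing potential to use highly effective contraception for at least a month either side of dosing: "Standard birth control methods are considered to be: oral or implanted contraceptive therapy and intra-uterine devices". Protocol 5.3.1, exclusion 9, bars medication in the 14 days before the first dose, "except for hormonal contraceptives in female".

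**On study.** Protocol 5.3.2 says "Any concomitant medications (including non-prescription medication, multi-vitamin preparations or herbal medications) are prohibited during the whole study", from Screening to Follow-Up. Protocol 5.3.3 item 8 lists "Use of any ongoing or concomitant medication" among the reasons for which the Investigator may withdraw a subject. Neither names an exception. SAP 14 defines concomitant treatment as anything other than investigational product taken during the study.

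**Analysis.** Protocol 11.2 covers "The data from subject(s) who received concomitant medication(s) or experienced diarrhea or vomiting during PK blood sampling periods", continues "which could render the plasma concentration-time profile unreliable as stated on section 5.3.3, may be excluded" for that period, and adds "The decision to exclude is made before bioanalysis". Its next paragraph includes all subjects with valid primary endpoints in both periods, and says that concentrations of subjects "withdrawn from the study due to adverse events or as list on section 5.3.3 will not be used for statistical evaluation". SAP 10.1 lists important deviations, among them receipt of an excluded concomitant medication, failure to withdraw someone who develops a withdrawal criterion, and out-of-window sampling. SAP 10.2 limits the PK set to subjects without deviations relevant to PK. SAP 12.2.2 refers to 10.1 for exclusion reasons.

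**The concern.** A woman who meets inclusion 10 with a pill or implant takes a medication through both sampling periods. The only written exemption ends at the first dose. Because Screening falls within 21 days before dosing, 5.3.2 and exclusion 9 disagree even about the pre-dose fortnight. Taken literally, she meets withdrawal item 8. If withdrawn, her data are not used. If kept, she looks like an important deviation. Losing one period loses the subject, because the analysis needs both.

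The 20% rule guarantees at least ten women, the drop-out allowance is four, and nobody is replaced. Five exclusions would therefore take the set below 44. At stake would be power and a primary set open to dispute.

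Two related gaps seemed to widen the problem. Out-of-window draws are on the list to which SAP 12.2.2 points. Vomiting or diarrhea in Period 2, without withdrawal, is left to discretion in a clinic that knows the treatment.

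**Working it through.** **1. Does the text force exclusion?** Taking each step in turn:

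- *Withdrawal.* Protocol 5.3.3 opens by saying the Investigator *may* withdraw; SAP 12.1 repeats this. Keeping a contraceptive user is within the text.
- *Deviation.* SAP 10.1 speaks of subjects who *develop* a withdrawal criterion on study. Contraception in place a month before dosing and accepted at entry does not fit that naturally. Its reference to an *excluded* medication implies that some medication is not excluded.
- *PK exclusion.* Protocol 11.2 also says *may*, and its unreliability qualifier follows all three triggers. The default keeps subjects with valid endpoints in both periods.
- *PK set.* An important deviation is not in itself an exclusion; SAP 10.2 asks whether it is relevant to PK. SAP 14 defines a term for recording and removes no one.

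**2. The plan's own figure.** Protocol 11.3 states that 44 evaluable subjects give at least 90% power for ratios from 0.95 to 1.05. The CV is redacted, so I solve for it.

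- Protocol formula, ratio 0.95, distance to the nearer limit: ln(0.95/0.80) = 0.1719 and (1.2816 + 1.6449)² = 8.564. Then s_w² = 44 × 0.1719² / (2 × 8.564) = 0.0759, and CV = √(e^0.0759 − 1) = 28.1%.
- Exact two one-sided tests: the highest CV giving 90% at N = 44 and ratio 0.95 is 27.5%.

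The claim is plausible but cannot be verified.

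**3. Power if users were excluded anyway.** Inputs: limits 0.80 to 1.25, one-sided α 5%, true ratio 0.95, SE = s_w√(2/N), N − 2 degrees of freedom. At CV 27.5%, s_w² = ln(1 + 0.275²) = 0.0729 and s_w = 0.270; for N = 44, SE = 0.270 × √(2/44) = 0.0576. Power is the probability that the 90% interval lies inside the limits. CVs of 20% and 27.5% and the numbers excluded are assumptions.

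| Excluded | N left | CV 20% | CV 27.5% |
|---|---|---|---|
| 0 | 48 | 99.4% | 92.3% |
| 4 | 44 | 99.1% | 90.1% |
| 5 | 43 | 99.0% | 89.4% |
| 10 | 38 | 98.1% | 85.6% |
| 15 | 33 | 96.4% | 80.3% |
| 24 | 24 | 89.6% | 65.0% |
| 38 | 10 | 44.2% | 14.4% |

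The number of women is at least 0.20 × 48 = 9.6, so 10, and at most 48 − 10 = 38. Users could be anywhere from 0 to 38, since intra-uterine devices, postmenopausal status and sterilization also qualify. At CV 27.5%, power stays above the cited 80% minimum until more than 15 are excluded.

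**4. Out-of-window draws.** Protocol 9.3 and SAP 8 say these are analysed at the actual time. No passage excludes the subject. The SAP 12.2.2 cross-reference to the deviation list is loose and does not override those two rules.

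**5. Period 2 vomiting or diarrhea.** At assumed rates of 1%, 3% and 5%, the expected number among 48 is 0.5, 1.4 and 2.4. Simulations (60,000 runs per setting, CV 15 to 27.5%, one or two events, exposure cut by 8 to 50%, events falling at random on either product) gave false bioequivalence at ratio 0.80 of 4.8 to 5.1%, whether affected subjects were kept or dropped. The largest power difference was 2.1 points (two events, exposure halved, CV 27.5%: 88.9% kept, 91.0% dropped). Only the contrived case with every kept event on Reference and an 8% cut exceeded this range of false bioequivalence, at 5.2 to 6.3%.

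**The case for a change.** The strongest counter-argument is that discretion over the primary set is itself the defect. The authors wrote the exemption once and left it out of 5.3.2, 5.3.3, 11.2 and SAP 14. Item 8 carries no qualifier, and within 5.3.3 the unreliability wording attaches to diarrhea alone, so reading it across to medication in 11.2 is an interpretation. No decider is named, and a literal reader could withdraw women who entered correctly. One sentence would close the gap.

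Much of this stands as a description. Protocol 5.3.2 does contradict exclusion 9 and sits badly with inclusion 10. Reconciling those clinical passages is for the sponsor. It does not follow that the analysis set is at risk. A literal reading would have the trial expel women for using a method that its own inclusion criterion names as standard. The specific entry rule is the sensible guide to the general ban, and nothing in the analysis rules prevents that reading.

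The wider remedies do not help. Automatic exclusion for any other medication during sampling would replace a judgement about profile reliability with a rule that can itself shrink the set. A named decider, a signed listing and a rerun of the ANOVA with excluded subjects restored are reporting preferences, given that exclusions are already decided before bioanalysis.

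**Conclusion.** No change to the analysis plan follows. The missing exemption is a wording gap that site and analysts would fill in the same way, by keeping women on contraception that the entry criteria allow. The primary result would then be unaffected.

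If users were excluded despite this, the cost would be power: 2.9 points for five users (92.3% to 89.4%) and 6.7 points for ten (92.3% to 85.6%) at the highest compatible CV, and at most 1.3 points for either at CV 20% (99.4% to 98.1%). Power below 80% needs more than 15 exclusions at CV 27.5%. False bioequivalence is not raised, because contraceptive use would normally be the same in both periods and exclusions are decided without concentration data.

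This rests on an unknown number of users, a redacted CV, and the permissive reading of 5.3.3 and 11.2, which their wording supports. Out-of-window draws are already settled, and the Period 2 discretion has little effect on either error rate when events are unrelated to product.
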